7.3.2 Exposures

The following exposures of interest are captured in this study

Table 2 Exposures of interest

	Cohort	When is measured
Glucocorticoids used in COVID-19 indication	All	At diagnosis index date and follow-up
Glucocorticoids for pre-existing conditions	Only in prevalent users' cohort	Before diagnosis index date
Other COVID-19 treatments: 
 • antiviral therapy (AV) • antibiotic therapy (AB) • immune-based therapy (IB) • antithrombotic therapy (AT) • anti-hypertensives (AH) • statins (S) • anti-diabetic (AD) (see Appendix 3)	All	At diagnosis index date and during follow-up
Oxygen therapies	All	At diagnosis index date and during follow-up*

* During follow-up this will be considered as an outcome

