7.3.2.1 Glucocorticoids

Glucocorticoids used in COVID-19 indication

The primary treatment group of interest is based on exposure to systemic glucocorticoids. The following drugs will be considered as being used for COVID-19 diagnosis:

- Dexamethasone (H02AB02)
- Prednisone (H02AB07)
- Prednisolone (H02AB06)
- Methylprednisolone (H02AB04)
- Hydrocortisone (H02AB09)

Only glucocorticoids which were investigated in clinical trials (13,21) or are recommended by clinical guidelines are included (22–24) to avoid misclassification of steroids used for other conditions. As indication is not captured in the available databases, a glucocorticoid treatment will be considered to have been initiated for COVID-19 treatment if:

For incident users

- The glucocorticoid treatment was initiated between 2 before and 30 days after COVID-19 diagnosis date (21)
- It is one of the five glucocorticoids recommended for COVID-19 as above

For prevalent users

- The glucocorticoid treatment was initiated between 2 before and 30 days after COVID-19 diagnosis date
- It is one of the five glucocorticoids recommended for COVID-19 as above
- The glucocorticoid started after COVID-19 diagnosis differs from the chronically used glucocorticoids OR there is a change in dose or schedule of administration compared to the prevalent use, occurred after COVID-19 diagnosis.

Glucocorticoids for pre-existing conditions

For the prevalent users, any steroid in the ATC class H02 glucocorticoids for systemic use will be considered. A patient is defined as a systemic glucocorticoids prevalent user if it has at least one prior exposure to systemic² glucocorticoids in the 120 days prior to diagnosis index date.

For the description of prevalent users of glucocorticoids, categories of use will be created based on proportion of days covered (PDC) during the lookback period. PDC is calculated as the number of days in period covered by prescriptions divided by number of days in the period.

- PDC > 85% as heavy user
- PDC 50-85% as moderate user
- less than 50% PDC as light user

Another categorization of prevalent glucocorticoids user will be based on how recently in the past the last prescription was observed:

- current use (concomitant on date of COVID-19 diagnosis)
- recent use (between 15-30 days before date of COVID-19 diagnosis)
- remote use (use ended more than 30 days before date of COVID-19 diagnosis)

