Steroids often have adjusted dose regimens such that drug may be slowly increased or decreased over time and short acute treatment episodes are also possible. Such changes in dose over time will not be examined, however total cumulative dose will be examined in relation to outcomes of interest (see below).

Cumulative dose

For glucocorticoids used in COVID-19 indication, orally administered, if quantity is available, the formula to calculate the cumulative exposure in mg is described below:

$$Cumulative\ dose_{solid}[mg] = \sum_{all\ exposures} quantity \times amount_value [mg]$$

If the **quantity is missing**, the number of units per day for solid formulations are extracted. The cumulative exposure in mg can then be calculated using the following formula:

$$Cumulative\ dose_{solid}[mg] = \sum_{exposures} units\ per\ day \times amount_value [mg] \times duration$$

For intravenous administration (bolus administration), the dose administered each time will be counted.

$$Cumulative\ dose\ intravenous [mg] = \sum_{all\ exposures} amount_value [mg]$$

Exposure groups for incidence calculation (secondary objective 2 and 3)

For the incidence rates calculation, an on-treatment exposure will be considered with mutually exclusive groups to allow calculation of incidence rates.

Each person will be classified as belonging to one of the following mutually exclusive exposure groups at treatment index date following COVID-19 diagnosis:

- Use of systemic glucocorticoids without other treatments for COVID-19 (drug and respiratory support)
- Use of systemic glucocorticoids plus other treatments for COVID-19 (drug and respiratory support)
- Only other treatments and respiratory support with no systemic glucocorticoids

- No specific treatments for COVID-19 infection (other concomitant treatments for indications other than for COVID-19 are allowed)

A single prescription would be enough to consider the patient as exposed. See section 7.3.2.1 for description of 'other treatment for COVID-19' that are included.

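### In prevalent users, patients who continue their usual systemic glucocorticoid unchanged fall into exposure group 3 or 4, so group 3's steroid-free label is untrue and the rates mix exposed and unexposed patients

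*Protocol*

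**What the plan says.** Protocol section 7.3.2.1 makes a patient a prevalent user on "at least one prior exposure to systemic² glucocorticoids in the 120 days prior to diagnosis index date", from any drug in ATC class H02. It foresees that some of these patients are still on the drug at diagnosis, under the category "current use (concomitant on date of COVID-19 diagnosis".

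Because indication is not recorded, the same section uses a rule to decide when a prevalent user's glucocorticoid counts as COVID-19 treatment. It must be one of five listed drugs, be initiated from 2 days before to 30 days after diagnosis, and meet a further condition: "The glucocorticoid started after COVID-19 diagnosis differs from the chronically used glucocorticoids OR there is a change in dose or schedule of administration".

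Section 7.2.3 ties the treatment index date to the start of the first glucocorticoid episode given specifically for COVID-19, for naive and prevalent users alike.

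Section 7.3.2.3 then requires each person to be in one of four mutually exclusive groups. Groups 1 and 2 use systemic glucocorticoids, without or with other COVID-19 treatments. Group 3 is "Only other treatments and respiratory support with no systemic glucocorticoids". Group 4 has no specific COVID-19 treatment, but "other concomitant treatments for indications other than for COVID-19 are allowed". Section 7.7.4 repeats the four groups and in its first list describes group 3 as having no steroids.

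Table 2 in section 7.3.2 gives the measurement time for glucocorticoids used for pre-existing conditions as "Before diagnosis index date".

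**The concern.** Secondary objective 2 quantifies events that glucocorticoids themselves may cause, such as infection, hyperglycaemia, hypertension and gastrointestinal bleeding. It does so by exposure group within naive and prevalent users. The group labels therefore tell the reader whether a rate was observed on or off a glucocorticoid.

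Among prevalent users the rules do not deliver that. Someone taking the same systemic glucocorticoid before and after diagnosis has started nothing and changed nothing for COVID-19, so the only groups left are 3 and 4. A group 3 rate in this stratum would be published as steroid-free while part of its person-time is on a steroid. If glucocorticoids raise the event rate, the group 3 and 4 rates are too high for an unexposed group. A reader looking across the rows could then conclude that glucocorticoid treatment adds little.

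**Working it through.** The protocol states no rate or count on this point, so there is no figure to reproduce. The check is a trace of the rules, followed by an illustration of size.

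**Trace of one patient.** Take a prevalent user on a stable regimen of a systemic glucocorticoid, continued unchanged through diagnosis.

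1. Section 7.3.2.1: the patient is a prevalent user with current use. The regimen is neither a different drug nor a changed dose or schedule, so it is not COVID-19 treatment.
2. Section 7.2.3: with no COVID-19 glucocorticoid episode, the patient has no treatment index date as defined, and has nothing that qualifies for groups 1 or 2.
3. Section 7.3.2.3: the patient must still be in one of the four groups. Without other COVID-19 treatment, that is group 4, whose wording admits drugs for other indications and does not except glucocorticoids. With other COVID-19 treatment or respiratory support, only group 3 remains, and its label is contradicted.

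**Does another provision catch this patient?**

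- Stratification (7.7.4) is by setting, user type, treatment group and subgroup. The mixture lies inside the prevalent stratum. The current/recent/remote and proportion-of-days-covered categories are not listed as strata for the rates.
- Censoring (7.3.2.3, 7.7.4) is triggered by a switch. Unchanged continuation is not a switch.
- Table 2 measures background glucocorticoids only before diagnosis, so later use is not captured as an exposure.
- The sensitivity analysis in 7.7.8 drops patients with short-term (14-day) prior use. Longer-term users remain, who are if anything more likely to be continuing.
- The propensity score (7.7.5) uses drug groupings from pre-index windows and may reflect recent glucocorticoid use. It cannot correct a crude rate or a group label.

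**Illustration of size.** Let c be the share of group 3 or 4 person-time in prevalent users spent on a continued glucocorticoid, and R the event rate ratio on versus off the drug. Neither is in the protocol; both are assumptions.

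Observed rate ÷ unexposed rate = (1 − c) + cR = 1 + c(R − 1).

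| | c = 0.3 | c = 0.6 |
|---|---|---|
| R = 1.5 | 1 + 0.3 × 0.5 = 1.15 | 1 + 0.6 × 0.5 = 1.30 |
| R = 2.0 | 1 + 0.3 × 1.0 = 1.30 | 1 + 0.6 × 1.0 = 1.60 |

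Over a wider range the factor runs from 1 + 0.1 × 0.25 = 1.025 (c = 0.1, R = 1.25) to 1 + 0.8 × 2.0 = 2.60 (c = 0.8, R = 3).

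Read informally side by side, a true ratio of 2.0 would look like 2.0/1.3 = 1.54 at c = 0.3 and 2.0/1.6 = 1.25 at c = 0.6. This last step also assumes that background and COVID-19 courses carry the same R.

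**The case against.** The strongest reply is that this is a labelling ambiguity and not a biased comparison. Several parts of it stand.

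- **Group 4 is not mislabelled.** It openly allows treatment for other indications. Only group 3 claims to be free of systemic glucocorticoids.
- **Other readings exist.** Taken literally, group 3's label keeps continuing users out. Section 7.3.2.3 also says one prescription suffices for exposure, so a repeat prescription might place them in groups 1 or 2. Neither reading works: the first leaves continuing users on other treatments in no group although everyone must be classified, and the second overrides the change-of-drug-or-regimen condition in 7.3.2.1. The sections need reconciling whichever is meant.
- **No comparison is planned.** Section 6.3 puts comparison of treated with untreated patients out of scope, 7.9.1 repeats that none will be done, and the Cox models in 7.7.4 are fitted within each group. A reader might infer that a steroid-free reference group is contaminated and a treatment effect biased. The protocol does not support that: 7.7.8 mentions a reference group but never says which group it is, and no between-group ratio is a stated estimand.
- **Naive users.** A reader might also infer that naive patients in groups 3 and 4 stay there after starting an unlisted glucocorticoid, or any glucocorticoid after day 30. That is not established. Patients are censored on switching treatment, including to another glucocorticoid, which may cover such starts; the text does not say.
- **Extent.** One exposure in 120 days makes a prevalent user, so many may have stopped before diagnosis. Current use at diagnosis and high coverage in the lookback period do not prove use during follow-up.

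What survives is the untrue group 3 label and the mixture of exposed and unexposed patients in groups 3 and 4 of the prevalent cohorts.

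**Conclusion.** The point holds in this limited form. Under sections 7.2.3, 7.3.2.1 and 7.3.2.3 taken together, prevalent users who continue their glucocorticoid unchanged end up in group 4, or in group 3 against its own label. Crude and adjusted steroid adverse-event rates for those groups in prevalent users then describe a mixture. No existing stratum, censoring rule or sensitivity analysis separates it.

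The direction is upward whenever R exceeds 1. The size is unknown: 1.15- to 1.6-fold under the central assumptions, and anywhere from negligible to more than twofold under wider ones. The damage is to the meaning of the labelled rates and to reading them side by side, not to a planned comparison. The primary objective does not rest on these groups. It should be corrected before the objective 2 and 3 analyses are run.

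**What to change.** 1. In 7.3.2.3 and both group lists of 7.7.4, state that groups 1 and 2 mean a systemic glucocorticoid started or changed for COVID-19 as defined in 7.3.2.1.
2. In the prevalent cohorts, split groups 3 and 4 by whether a prescription for any H02 glucocorticoid covers the start of follow-up. Reserve the label for no systemic glucocorticoids for uncovered patients, and report covered patients as continuing a background glucocorticoid.
3. Define that start date. The treatment index date in 7.2.3 exists only for patients who start a COVID-19 glucocorticoid, so groups 3 and 4 need the diagnosis index date or another stated date.
4. State that censoring at switch, for patients in the glucocorticoid-free category, includes the first record of any systemic H02 glucocorticoid. This also settles the open question for naive users.

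The cost is small. Current use at diagnosis is already derived for the primary objective. H02 use after diagnosis needs one added derivation, because Table 2 stops at diagnosis. The drawback is smaller cells in the prevalent-user tables.

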7.3.2.2 Other COVID-19 treatments

Additional distinct treatment cohorts will be created based on use of other drugs that might be used as treatment of COVID-19 according to various guidelines. Patients will be considered exposed to other pharmacotherapeutic treatments for COVID-19 if available prescription data are available and if the drugs are in the list below.

- a) antiviral therapy (AV);
- b) antibiotic therapy (AB)
- c) immune-based therapy (IB)
- d) antithrombotic therapy (AT)
- e) anti-hypertensives (AH)
- f) statins (S);
- g) anti-diabetics (AD);

² Systemic effects of inhaled and topical use of glucocorticoids is considered low and therefore use will not be considered for this study

These treatments were identified and classified through systematic review of CDC treatment guidelines, clinicaltrials.gov, or clinical guidelines, as part of another OHDSI project. (25) The full list of products is available in Appendix 3.

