Only the first episode of exposure will be considered, patients being censored when they switch to another treatment (including switch to another glucocorticoid) or when follow up ends. Duration of follow-up for each treatment cohort will be summarized and will constitute the denominator for calculation of effect estimates. A persistence window of 7 days between drug utilization records for each study drug will be allowed considered as continuous exposure for the outcome's assessment.

In case that more than 70% of the patients are censored, a sensitivity approach will be applied for objectives 2 and 3 (see Section 7.7.8).

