LPD Italy is comprised of anonymised patient records collected from software used by GPs during an office visit to document patients' clinical records. Data coverage includes over 2M patient records with at least one visit and 119.5M prescription orders across 900 GP practices. Dates of service include from 2004 through present. Observation time is defined by the first and last consultation dates. Drugs are captured as prescription records with product, quantity, dosing directions, strength, indication and date of consultation.

Integrated Primary Care Information (IPCI), The Netherlands

IPCI is collected from EHR records of patients registered with their GPs throughout the Netherlands. The selection of 391 GPs is representative of the entire country. The database contains records from 2.6 million patients out of a Dutch population of 17M (8.2%) starting in 1996. The median follow-up is 2.2 years. The observation period for a patient is determined by the date of registration at the GP and the date of leave/death. The observation period start date is refined by many quality indicators, e.g. exclusion of peaks of conditions when registering at the GP. All data before the observation period is kept as history data. Drugs are captured as prescription records with product, quantity, dosing directions, strength and indication. Drugs not prescribed in the GP setting might be underreported. Indications are available as diagnoses by the GPs and, indirectly, from secondary care providers but the latter might not be complete. Approval needs to be obtained for each study from the Governance Board. (5) The IPCI database is currently increasing the update frequency because of the COVID-19 pandemic (now updated till March 2020).

Information System for Research in Primary Care (SIDIAP), IDIAP Jordi Gol (Spain)

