Appendix 3 Alternative treatments for COVID-19

Treatment	
Antiviral therapy (AV)	
P01BA02	Hydroxychloroquine
	Hydroxychloroquine + azithromycin combination
	Hydroxychloroquine + fluoroquinolones combination
	Hydroxychloroquine + amoxicillin combination
	Hydroxychloroquine + ceftriaxone combination
P01BA01	Chloroquine
P02CF01	Ivermectin
J02AC02	Itraconazole
J05AX27	Favipiravir
Not yet assigned	Remdesivir
J05AP01	Ribavirin
J05AH02	Oseltamivir
J05AR10	Lopinavir + ritonavir combination
J05AF09	Emtricitabine
G03XC01	Raloxifene
Antibiotic therapy (AB)	
J01CA04	Amoxicillin
J01MA01	Ofloxacin
J01MA02	Ciprofloxacin
J01MA03	Pefloxacin
J01MA04	Enoxacin
J01MA05	Temafloxacin

J01MA06	Norfloxacin
J01MA07	Lomefloxacin
J01MA08	Fleroxacin
J01MA09	Sparfloxacin
J01MA10	Rufloxacin
J01MA11	Grepafloxacin
J01MA12	Levofloxacin
J01MA13	Trovafloxacin
J01MA14	Moxifloxacin
J01MA15	Gemifloxacin
J01MA16	Gatifloxacin
J01MA17	Prulifloxacin
J01MA18	Pazufloxacin
J01MA19	Garenoxacin
J01MA21	Sitafoxacin
J01MA22	Tosufloxacin
J01MA23	Delafloxacin
J01DD04	Ceftriaxone
J01FA10	Azithromycin
Immune-based therapy (IB)	
L04AC07	Tocilizumab
L04AC14	Sarilumab
L04AC11	Siltuximab
L04AA37	Baricitinib
L04AA29	Tofacitinib
L04AB04	Adalimumab

L04AB01	Etanercept
L04AB02	Infliximab
L04AC05	Ustekinumab
L04AC03	Anakinra
L01XE27	Ibrutinib
L01XE18	Ruxolitinib
L01XC07	Bevacizumab
L04AA27	Fingolimod
L04AA25	Eculizumab
L04AX02	Thalidomide
L04AD02	Tacrolimus
L03AB02	Interferon Beta Natural
L03AB07	Interferon Beta-1a
L03AB08	Interferon Beta-1b
L03AB13	Peginterferon Beta-1a
L03AB15	Ropeginterferon Alfa-2b
L03AB12	Albinterferon Alfa-2b
L03AB14	Cepeginterferon Alfa-2b
L03AB01	Interferon Alfa Natural
L03AB04	Interferon Alfa-2a
L03AB05	Interferon Alfa-2b
L03AB06	Interferon Alfa-N1
L03AB09	Interferon Alfacon-1
L03AB11	Peginterferon Alfa-2a
L03AB10	Peginterferon Alfa-2b
L03AA09	Sargramostim

A11CC05	Colecalciferol
A02BA01	Cimetidine
A02BA02	Ranitidine
A02BA03	Famotidine
A02BA04	Nizatidine
A02BA06	Roxatidine
Antithrombotic therapy (AT)	
B01AA01	Dicoumarol
B01AA07	Acenocoumarol
B01AA03	Warfarin
B01AB01	Heparin
B01AB05	Enoxaparin
B01AB04	Dalteparin
B01AB12	Bemiparin
B01AB06	Nadroparin
B01AB07	Parnaparin
B01AB08	Reviparin
B01AB09	Danaparoid
B01AB10	Tinzaparin
B01AB11	Sulodexide
B01AB51	Heparin Combinations
B01AC01	Ditazole
B01AC02	Cloricromen
B01AC03	Picotamide
B01AC04	Clopidogrel

B01AC05	Ticlopidine
B01AC06	Acetylsalicylic Acid
B01AC07	Dipyridamole
B01AC08	Carbasalate Calcium
B01AC09	Epoprostenol
B01AC10	Indobufen

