B01AC11	Iloprost
B01AC13	Abciximab
B01AC15	Aloxiprin
B01AC16	Eptifibatide
B01AC17	Tirofiban
B01AC18	Triflusal
B01AC19	Beraprost
B01AC21	Treprostinil
B01AC22	Prasugrel
B01AC23	Cilostazol
B01AC24	Ticagrelor
B01AC25	Cangrelor
B01AC26	Vorapaxar
B01AC27	Selexipag
B01AD01	Streptokinase
B01AD02	Alteplase
B01AD03	Anistreplase
B01AD04	Urokinase
B01AD05	Fibrinolysin

B01AD06	Brinase
B01AD07	Reteplase
B01AD08	Saruplase
B01AD09	Ancrod
B01AD10	Drotrecogin Alfa (Activated)
B01AD11	Tenecteplase
B01AD12	Protein C
B01AD02	Alteplase
B01AD11	Tenecteplase
B01AD07	Reteplase
B01AE01	Desirudin
B01AE02	Lepirudin
B01AE03	Argatroban
B01AE04	Melagatran
B01AE05	Ximelagatran
B01AE06	Bivalirudin
B01AE07	Dabigatran Etxilate
B01AF01	Rivaroxaban
B01AF02	Apixaban
B01AF03	Edoxaban
B01AF04	Betrixaban
B01AX01	Defibrotide
B01AX04	Dermatan Sulfate
B01AX05	Fondaparinux
B01AX07	Caplacizumab

B02AA01	Aminocaproic Acid
B02AA02	Tranexamic Acid
B02AB04	Camostat
J06BA01	Immunoglobulins, Normal Human, For Extravascular Adm.
J06BA02	Immunoglobulins, Normal Human, For Intravascular Adm.
L03AX03	BCG Vaccine
Antihypertensives (AH)	
C03AA01	Bendroflumethiazide
C03AA02	Hydroflumethiazide
C03AA03	Hydrochlorothiazide
C03AA04	Chlorothiazide
C03AA05	Polythiazide
C03AA06	Trichlormethiazide
C03AA07	Cyclopenthiiazide
C03AA08	Methyclothiazide
C03AA09	Cyclothiazide
C03AA13	Mebutizide
C08CX01	Mibefradil
C08DA01	Verapamil
C08DA02	Gallopamil
C08DA51	Verapamil, Combinations
C08DB01	Diltiazem
C08EA01	Fendiline
C08EA02	Bepridil
C09AA01	Captopril

C09AA02	Enalapril
C09AA03	Lisinopril
C09AA04	Perindopril
C09AA05	Ramipril
C09AA06	Quinapril
C09AA07	Benazepril
C09AA08	Cilazapril
C09AA09	Fosinopril
C09AA10	Trandolapril
C09AA11	Spirapril
C09AA12	Delapril
C09AA13	Moexipril
C09AA14	Temocapril
C09AA15	Zofenopril
C09AA16	Imidapril
C09CA01	Losartan
C09CA02	Eprosartan
C09CA03	Valsartan
C09CA04	Irbesartan
C09CA05	Tasosartan
C09CA06	Candesartan
C09CA07	Telmisartan
C09CA08	Olmesartan Medoxomil
C09CA09	Azilsartan Medoxomil
C09CA10	Fimasartan

Statins (S)	
C10AA01	Simvastatin
C10AA02	Lovastatin
C10AA03	Pravastatin
C10AA04	Fluvastatin
C10AA05	Atorvastatin
C10AA06	Cerivastatin
C10AA07	Rosuvastatin
C10AA08	Pitavastatin
Antidiabetic (AD)	
A10BA02	Metformin
A10BH01	Sitagliptin
A10BH02	Vildagliptin
A10BH03	Saxagliptin
A10BH04	Alogliptin
A10BH05	Linagliptin
A10BK01	Dapagliflozin
A10BK02	Canagliflozin
A10BK03	Empagliflozin
A10BK04	Ertugliflozin
A10BJ01	Exenatide
A10BJ02	Liraglutide
A10BJ03	Lixisenatide
A10BJ04	Albiglutide
A10BJ05	Dulaglutide

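### Other COVID-19 treatment is defined by one prescription of any Appendix 3 drug with no new-start condition, so continuing users of long-term drugs are placed in the wrong exposure group

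*Protocol*

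**What the plan says.** Protocol 7.3.2.3 places each person in one of four mutually exclusive groups at the treatment index date:

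- group 1: glucocorticoids without other COVID-19 treatment
- group 2: glucocorticoids with other COVID-19 treatment
- group 3: other treatment or respiratory support, no glucocorticoid
- group 4: no COVID-19 treatment

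Other treatment is defined in 7.3.2.2, where patients are "considered exposed to other pharmacotherapeutic treatments for COVID-19 if available prescription data are available and if the drugs are in the list below". The threshold in 7.3.2.3 is: "A single prescription would be enough to consider the patient as exposed". Table 2 measures these drugs at the diagnosis index date and during follow-up. Appendix 3 gives the products, among them "Atorvastatin" under statins and "Colecalciferol" under immune-based therapy.

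For glucocorticoids, 7.3.2.1 sets a stricter rule. It begins "As indication is not captured in the available databases" and then requires a start from 2 days before to 30 days after diagnosis. In prevalent users it also requires a different glucocorticoid or a change in dose or schedule.

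Group 4 has an exception: "other concomitant treatments for indications other than for COVID-19 are allowed". Section 7.3.2.3 also considers only the first exposure episode, with "patients being censored when they switch to another treatment (including switch to another glucocorticoid) or when follow up ends".

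**The concern.** The protocol recognises that, without a recorded indication, a prescription does not show what the drug was given for. It solves this for glucocorticoids with a start window and a change rule. It sets no such rule for the other drugs, although those drugs alone decide group 1 against group 2 and, with respiratory support, group 3 against group 4.

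Many Appendix 3 drugs are taken for years. A patient on a statin or an ACE inhibitor before the pandemic, who continues it unchanged and receives nothing for COVID-19, meets the definition of other treatment.

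What is at stake is the meaning of the group labels. Several of these drugs treat or mark risk for listed outcomes: hypertension, hyperglycaemia, gastric ulcer and bleeding, and the cardiovascular composite. If long-term users collect in groups 2 and 3, differences in reported rates between groups 1 and 2, or 3 and 4, partly reflect who had treated cardiometabolic disease beforehand. The Cox adjustment in 7.7.4 is made within each group, so it cannot correct wrong membership.

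**Working it through.** **Text check**

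1. Conditions for other treatment: a prescription record and a listed drug (7.3.2.2), one prescription being enough (7.3.2.3), measured at diagnosis and in follow-up (Table 2). No section requires a new start, a change or a period without prior use.
2. Long-term drugs in Appendix 3: eight statins; ACE inhibitors, ARBs and thiazides; metformin and other antidiabetics; acetylsalicylic acid and warfarin; colecalciferol; five H2-blockers.
3. The group 4 exception depends on indication, which 7.3.2.1 says is unavailable. The first group list in 7.7.4 also drops the indication qualifier, while the second keeps it.
4. Section 7.4 contradicts 7.3.2.1. For LPD Italy it says: "Drugs are captured as prescription records with product, quantity, dosing directions, strength, indication and date of consultation". The IPCI entry also names indication.
5. Section 7.3.2.3 refers to 7.3.2.1 for the description of other treatment, but that description is in 7.3.2.2.

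**Size**

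The protocol states no figure to reproduce. Two assumed inputs are needed:

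- c = share of patients on at least one long-term Appendix 3 drug
- t = share with genuine other COVID-19 treatment, including respiratory support

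Patients with genuine other treatment are correctly placed whatever else they take. With c and t independent:

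- misassigned share = c(1 - t)
- share labelled other-treated = 1 - (1 - c)(1 - t)
- part of that label due only to a chronic drug = c(1 - t) / [1 - (1 - c)(1 - t)]

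| c | t | misassigned | labelled | chronic-only part of label |
|---|---|---|---|---|
| 0.2 | 0.5 | 10% | 60% | 17% |
| 0.3 | 0.3 | 21% | 51% | 41% |
| 0.4 | 0.3 | 28% | 58% | 48% |
| 0.5 | 0.1 | 45% | 55% | 82% |
| 0.7 | 0.05 | 66.5% | 71.5% | 93% |

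For c = 0.4 and t = 0.3: 0.4 × 0.7 = 0.28; 1 - 0.6 × 0.7 = 0.58; 0.28 / 0.58 = 0.48.

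Independence matters. At the same c and t, if every genuinely treated patient were also a chronic user, the misassigned share would be 0.4 - 0.3 = 10%. If none were, it would be 40%.

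**Direction of the effect on rates (illustration)**

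Assume a 30-day event risk of 4% in chronic users and 1% in others, no treatment effect, c = 0.4 and t = 0.3, and take patients without glucocorticoids. With correct labels, groups 3 and 4 would both read 0.4 × 4% + 0.6 × 1% = 2.2%. Under the list rule, group 3 reads (0.40 × 4% + 0.18 × 1%) / 0.58 = 3.1%, where 0.18 = 0.6 × 0.3, and group 4 reads 1%. These risks are assumed and come from no document.

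**The case against.** The strongest reply is that the study is not comparative. Section 6.3 puts treatment comparisons out of scope, 7.9.1 warns that confounding must be considered in reading the rates, and the rates are also stratified by cardiovascular disease and type 2 diabetes. This limits the harm, and stratification removes part of the comorbidity difference. It does not make the labels correct: a group 3 rate is still reported as that of patients given other COVID-19 treatment.

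Four stronger readings are tempting, and the documents do not support them:

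- **That all four groups sort by chronic disease.** The glucocorticoid split uses the -2 to +30 day rule, and antivirals, antibiotics and respiratory support still count as treatment.
- **That groups 1 and 4 lose all patients with treated hypertension, diabetes or heart disease.** Appendix 3 lists no beta-blockers, loop diuretics, dihydropyridines, insulin or sulfonylureas; patients on only those drugs stay.
- **That refills will censor follow-up.** Section 7.3.2.3 censors on a switch to another treatment and bridges gaps of 7 days for the same drug. It does not call a refill of a long-term drug a switch. It does not exclude that reading either. An intention-to-treat analysis is planned in 7.7.8 if more than 70% are censored for switching.
- **That the immunotherapy reference group in 7.7.8 would be mostly vitamin D and H2-blocker users.** Both are in that class of Appendix 3, but no prescription counts are given.

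On respiratory support, Table 2 already treats oxygen therapy after diagnosis as an outcome and 7.3.2.3 fixes groups at the treatment index date. What remains is the interval between those dates, because 7.3.5 counts support on or after diagnosis.

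**Conclusion.** The point holds for the with/without-other-treatment split only: group 1 against 2, and group 3 against 4. Applied as written, the rule assigns continuing users of listed long-term drugs to the other-treatment groups, and the group 4 exception cannot be applied where indication is unavailable. The rates for secondary objectives 2 and 3 by this split then partly track treated cardiometabolic disease. The primary objective and the glucocorticoid split are not affected.

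The size cannot be read from the documents. Under independence it is c(1 - t): 28% at c = 0.4 and t = 0.3, and 10% to 66.5% over c = 0.2 to 0.7 and t = 0.05 to 0.5. The share of chronic users is not itself the share misassigned. The protocol itself fixes the list, the threshold and the censoring rule, so this should be corrected there.

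**What to change.** - **7.3.2.2 and 7.3.2.3:** count an Appendix 3 drug as other COVID-19 treatment only if newly started on days -2 to +30 around diagnosis, the window already used for glucocorticoids, with no ongoing use of the same drug before it. Apply the no-prior-use condition to the chronically used classes. For short-course drugs such as antibiotics use a shorter washout or none, since a long one would reject a genuine repeat course. Whole classes then need not be removed from the list.
- **Continuing drugs:** keep them as baseline covariates, and state that continuation or refill of a pre-existing drug is not a switch for censoring.
- **Respiratory support:** state that support up to the treatment index date defines the group and later support is only an outcome, reconciling Table 2, 7.3.2.3 and 7.3.5. Section 7.2.3 defines that date by glucocorticoid start, so name the day used for groups 3 and 4.
- **Indication:** reconcile 7.3.2.1 with 7.4 for LPD Italy and IPCI. Where indication is recorded, it can be used to check the new-start rule.
- **Consistency:** use one wording for group 4 in 7.3.2.3 and 7.7.4, and correct the cross-reference to 7.3.2.2.

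The cost is wording and a look-back step in the code. Groups 2 and 3 become smaller, so their rates become less precise. HM Hospitales has little history with which to identify prior use, so misassignment there would remain and should be stated as a limitation.
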